5. Meets DSM IV criteria for any major psychiatric disorder including psychosis, major depression and bipolar disorder.
6. Known history of or self-reported active alcohol and/ or substance abuse within the past three years.
7. Isolated living circumstances which would prohibit a study partner from providing sufficient and credible information about the participant.
8. Poorly controlled hypertension
9. Known Atrioventricular heart block, known heart block type I-III.
10. History of myocardial infarction or signs or symptoms of unstable coronary artery disease within the last year (including revascularization procedure/angioplasty).
11. Severe pulmonary disease (including chronic obstructive pulmonary disease) requiring more than 2 hospitalizations within the past year.
12. Untreated obstructive sleep apnea.
13. Any thyroid disease (unless euthyroid on treatment for at least 6 months prior to screening).
14. Active neoplastic disease (except for skin tumors other than melanoma) within five years.
15. Absolute lymphocytopenia of $<1,000/\text{mm}^3$, or a history of lymphocytopenia within the past two years.
16. Absolute neutropenia of $<1,000/\text{mm}^3$, or a history of neutropenia within the past two years.
17. History of/ or current thromboembolism (including deep venous thrombosis).
18. Any clinically significant hepatic or renal disease (including presence of Hepatitis B or C surface antigen or an elevated transaminase levels of greater than 2x the upper limit of normal (ULN) or creatinine greater than 1.5 x upper limit of normal (ULN)).
19. Clinically significant hematologic or coagulation disorder including any unexplained anemia, or a platelet count less than $100,000/\mu\text{L}$ at screening.
20. Use of any investigational drug within 30 days or within five half-lives of the investigational agent, whichever is longer.
21. Unwilling or unable to undergo CT or MRI imaging.
22. In the opinion of the investigator, participation would not be in the best interest of the subject.
23. Subjects with CYP2C9*3/*3 genotyping

*Waiver/exemption requests for Inclusion/Exclusion Criteria may be submitted to the medical monitor for review and approval on an individual basis.

Phase:

IIb

Description of Sites/Facilities Enrolling Participants:	This is a single site study located at Barrow Neurological Institute in Phoenix, Arizona.

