For safety reasons, a gradual dose escalation regimen will be implemented for mild AD dementia subjects receiving Siponimod/Placebo. The medication will be administered in 0.25 mg increments biweekly reaching the maximum dose of 1 mg. As a precaution, the initial higher doses will be given in a clinical setting, with subjects observed for six hours by study staff who are blinded to the study drug. This allows for prompt intervention in case of any distress, such as issues with heart or blood pressure. During these in-person visits, blood samples will be collected to monitor for signs of toxicity changes. Tests will include a complete blood count with differential, comprehensive metabolic panels, and liver function.

All test results will be reviewed by the principal investigator (or sub-investigators) to determine whether toxicity is developing in study subjects. Moreover, we will carry out cognitive tests every 3 months and volumetric MRI every 6 months (Table 1) to detect eventual brain toxicities. Finally, in case of AEs outside of the clinic, Study subjects will be provided contact information for both clinic and study coordinator.

The investigator or his designee is responsible for explaining the correct use of the investigational agents to the patient/caregiver/study partner, verifying that instructions are followed properly per drug manufacturer. Study staff will maintain accurate records of investigational product dispensing and collection and returning all unused medication to the Study Site at each in-person visit. Patients will be instructed to contact the investigator or the study coordinator as soon as possible if he or she has a complaint or problem with the investigational product so that the situation can be assessed.

If toxicities are identified, we will apply a special toxicity protocol. Per clinical trials, hepatotoxicity was primarily noted in controlled trials of Siponimod in patients. Notably, AST and ALT values were elevated above 3 times the upper limit of normal. If hepatotoxicity is noted, the subject will be withdrawn from the study and not replaced if this occurs after Visit 7. Please refer to the section, Procedure Used in Case of Toxicity.

PREPARATION/HANDLING/STORAGE/ACCOUNTABILITY

ACQUISITION AND ACCOUNTABILITY

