A complete physical examination (with neurological exam) will be performed at the visits listed in the study protocol and schedule of events. An abbreviated physical examination, to include an ophthalmic examination and routine examination of the heart, lungs, abdomen, skin, and oral cavity, will also be performed. Sitting vital signs (blood pressure, heart rate, respiratory rate, and temperature), after each subject sits quietly for at least 5 minutes, and body weight will be assessed at the Screening Visit and at each subsequent visit.

+ Vital Signs

Body temperature (oral or tympanic) will be measured as specified in the Schedule of Activities and as clinically indicated.

Blood pressure and pulse rate (PR) will be measured as specified in the Schedule of Activities and as clinically indicated. Blood pressure and PR should be measured after at least 5 minutes of sitting.

+ Body Weight and Height

Body weight and height will be recorded as specified in the Schedule of Activities and as clinically indicated.

+ Neurological Examination

A directed neurological examination will be performed by the investigator at the time points specified in the protocol and schedule of events.

Any clinically significant change from baseline on follow-up physical/neurological examinations should be recorded as an AE and reported in the CRF. If additional ARIA-H, ARIA-E, are detected, an additional neurological exam may be performed by the investigator.

- Toxicity Assessment

During visits at the study site, we will collect blood samples and conduct blood counts and comprehensive metabolic panels to monitor hematologic and metabolic toxicities. All lab results will be reviewed by the primary investigator, or sub-investigators, to determine if any clinically significant findings are seen that could be attributed to Siponimod related toxicities.

- Procedure Used in Case of Toxicity

If toxicities are identified, we apply a special toxicity protocol. The hematologic or chemistry values indicative of severe AEs are those listed in exclusion criteria.

If toxicity, including cardiac SAEs, is suspected, or proven, to be linked to Siponimod, subjects will stop taking the study drug for 7 days, and undergo new blood tests after at least 7 days of washout. If test results continue showing toxicity, subjects will be withdrawn from the study and not replaced if this occurs after Visit 7.

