If toxicity markers improve, subjects will resume dosing at the prior lower dose (i.e., toxic dose minus 0.25 mg) and remain on this regimen until the end of the study. In case of a second toxic event, dosing will again be stopped for 7 days, and blood tests conducted. If the test results continue showing toxicity, subjects will be withdrawn and not replaced if this occurs after Visit 7. If toxicity markers improve, subjects will resume dosing at the previous lower dose (i.e., toxic dose minus 0.25 mg) and remain at this lower dose until the end of the study.

In case of a third toxic event, subjects will be withdrawn and not replaced if this occurs after Visit 7. When study medication is withdrawn, study subjects will be recorded as “End Of Study Drug Visit” and undergo the corresponding assessments (Week 52 in Table 1). Then, the subjects will be asked to complete the corresponding washout period schedule of assessments: (Week 56 in Table 1) and 26 week “End of Study” (Week 78 in Table 1).

- Tolerability Assessment

Tolerability of Siponimod in study subjects will be derived from the frequency of AEs and study withdrawal motivated by subjects’ discomfort during the dosing period.

- Standard MRI (screening 1)

Patients who do not have an MRI scan within the past 12 months of Screening Visit Day 1 will be scheduled for an vMRI or CT during the screening period with results obtained before randomization is decided. (MRI is preferred).

>> Routine MRI Scan (default choice)

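### Section 8 withdraws a subject for hepatotoxicity, but the Section 10 procedure it cites allows up to two re-exposures; neither says which governs, and Section 8 sets no transaminase trigger

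*Protocol*

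**What the plan says.** Section 8, Dosing and Administration, gives a direct rule: "If hepatotoxicity is noted, the subject will be withdrawn from the study and not replaced if this occurs after Visit 7". The sentence before it says that in earlier trials "AST and ALT values were elevated above 3 times the upper limit of normal". The sentence after it is a cross-reference: "Please refer to the section, Procedure Used in Case of Toxicity".

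The procedure referred to, in Section 10, takes its laboratory limits from the entry criteria: "The hematologic or chemistry values indicative of severe AEs are those listed in exclusion criteria". For transaminases that is exclusion criterion 18 in the Section 1 synopsis, which bars subjects with "elevated transaminase levels of greater than 2x the upper limit of normal (ULN". When toxicity is thought or shown to be due to siponimod, "subjects will stop taking the study drug for 7 days, and undergo new blood tests after at least 7 days of washout". If the retest still shows toxicity, the subject is withdrawn. If markers improve, "subjects will resume dosing at the prior lower dose (i.e., toxic dose minus 0.25 mg) and remain on this regimen". The same hold, retest and step down follow a second event. Only then: "In case of a third toxic event, subjects will be withdrawn".

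**The concern.** A reader who stops at Section 8 takes the subject out. A reader who follows its cross-reference holds drug for a week and, if the retest is better, gives the drug again. Both have followed the protocol. Liver injury is one of the serious risks listed in Section 3.1.1, and safety is the primary objective, so the action on a liver signal should not depend on which section the investigator has open.

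The trigger is also incomplete. Section 8 acts on hepatotoxicity but does not say what laboratory result counts as hepatotoxicity.

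What is at stake is subject safety and consistent handling. No hypothesis test depends on this rule, and laboratory changes are tabulated under Section 12 whatever action is taken.

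**Working it through.** The protocol states no figure on this point to reproduce. The check sets the two rules side by side and traces the dose steps.

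**Action on a liver finding**
- Section 8: withdraw. No hold, retest or resumption is mentioned.
- Section 10: hold, retest, and resume 0.25 mg lower if improved; repeat once; withdraw if a retest still shows toxicity or at a third event.
- Scope: Section 10 expressly includes chemistry values and exempts no organ, so liver results fall under it.
- Precedence: neither section states it. The cross-reference does not settle it, because the section it points to gives a different action.

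**Re-exposures possible under Section 10**

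With starting dose d (mg), a step of 0.25 mg and at most two resumptions, the number is min(2, d/0.25 − 1):
- d = 1.00: min(2, 3) = 2. The doses are 1.00 − 0.25 = 0.75 mg, then 0.75 − 0.25 = 0.50 mg; a third event means withdrawal.
- d = 0.75: min(2, 2) = 2 (0.50 mg, then 0.25 mg).
- d = 0.50: min(2, 1) = 1 (0.25 mg; the next step would be 0).
- d = 0.25: min(2, 0) = 0.

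Under Section 8 the number is 0 at every dose. From Day 42 the planned dose is 1 mg, so for most of the treatment year the contrast is 0 against up to 2.

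**Trigger level**
- Above 2 and up to 3 times ULN: a severe-AE value by Section 10, and below the only level that Section 8 mentions.
- Above 3 times ULN: a severe-AE value by Section 10, and of the size that Section 8 describes from earlier trials without making it a criterion.
- The only numeric on-treatment level the protocol sets is therefore above 2 times ULN, through criterion 18.

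**How often it could arise**

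The protocol gives no hepatotoxicity rate. Table 2 gives transaminase increase in 11% on siponimod 2 mg and 3% on placebo, in MS patients, pooling several liver-test terms of any size. Applied to this trial: 0.11 × 70 = 7.7 siponimod subjects and 0.03 × 35 = 1.05 placebo subjects. If the drug rate is halved for the 1 mg dose (an assumption), 0.055 × 70 = 3.85. These counts show only that liver-test events are foreseeable. They do not estimate hepatotoxicity, and they are not a firm upper limit, since rates in this older population are unknown.

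**The case against.** The best defence is that a specific rule prevails over a general one: Section 8 singles out hepatotoxicity for withdrawal, and Section 10 deals with everything else. Alternatively, Section 8 is shorthand for the last step of Section 10, since both use the same clause about no replacement after Visit 7. These are both reasonable readings, but they lead to different actions, and the text does not choose between them.

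Safeguards also narrow the problem. Resumption needs improved markers and the hold needs a suspected or established link to the drug. There is one site, the investigators review all results, and the Medical Monitor and DSMB are told at once of moderate to severe events. This stands: it limits how often and how widely handling could diverge. It does not tell the investigator which rule to apply.

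Two stronger readings are tempting. A reader might infer that the protocol sets two competing thresholds, 2 and 3 times ULN. It does not, because the 3-times figure describes past trials. The defect is an undefined trigger.

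A reader might also infer that carrying exclusion criterion 15 (lymphocytes below 1,000/mm3) into treatment turns an expected drug effect into a severe AE. The protocol expects lymphocytes to fall, but it nowhere says that counts below 1,000 are expected. The hold depends on judged drug-related toxicity, and Section 11 leaves the severity of laboratory findings to clinical judgement. A cautious limit is defensible when Section 3.1.1 links low lymphocytes to serious infection, and dropping it without a replacement would remove the only numeric lymphocyte limit.

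**Conclusion.** The liver conflict holds on the current text. For the same finding, Section 8 allows no re-exposure and Section 10 allows up to two, at 0.75 mg and then 0.50 mg for a subject on 1 mg, with no statement of which governs and no trigger level in Section 8. The two re-exposures assume improved retests after the first and second events and a judged link to siponimod each time. The number of subjects concerned is unknown.

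This should be fixed for safety and consistency. It does not undermine any planned test. The lymphocyte limit is not an error; at most, the sponsor could confirm that criterion 15 is meant to apply on treatment, given that the haematologic holds named as examples under Safety Monitoring are thrombocytopenia and neutropenia.

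**What to change.** In Section 10, Procedure Used in Case of Toxicity, state that hepatotoxicity is an exception to the hold-and-resume steps and leads to withdrawal of study drug as in Section 8. The end-of-drug and washout assessments already listed there would follow.

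State one transaminase level for that rule in both sections. One workable form is to withdraw above 3 times ULN, and to apply the hold and dose reduction to drug-related values above 2 and up to 3 times ULN. The clinical team and Medical Monitor should choose the level.

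The cost is one short amendment, with no added visits, tests or tables. The small downside is that a few subjects whose values would have recovered on a lower dose may come off drug.

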Immuno-modulation is mostly achieved by preventing egression of lymphocytes from lymphoid organs, and the modulation of cytokine expression, including microglia⁵. For T lymphocytes, it was shown that S1PR modulators prevent the infiltration of CD8+ memory cells in the central nervous system (CNS). This property could be key for AD since, very recently, the group of Wyss-Coray showed that CD8+ T cells likely play a critical role in the adaptive immune response in the CNS of AD patients^{17,42}. On the other hand, the molecular mechanisms for neuroprotection are currently poorly understood. Nonetheless, both fingolimod and Siponimod lower the rate of brain atrophy in remitting relapsing MS (RRMS)⁷. Very interestingly, Siponimod was found to reduce brain atrophy at later stages of MS called secondary progressive MS (SPMS), making it the first drug with a demonstrated neuroprotective effect in SPMS¹². More precisely, at month 12 the percentage of total brain volume change from baseline adjusted mean were -0.28% and -0.46% ($p < 0.0001$) in Siponimod vs placebo-treated SPMS subjects, respectively²⁵.

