3. RISK/BENEFIT ASSESSMENT

3.1.1 KNOWN POTENTIAL RISKS

Siponimod (formerly known as BAF312 and completed trial NCT #01665144) has been FDA approved since 2019 (IND #076122) for the treatment of multiple sclerosis. Most adverse events have been reported from MS patients, and very little is known about possible adverse events in subjects without MS. Most risks are associated with doses >2 mg/day. Most common adverse reactions (reported in >5%) are headache, hypertension, and transaminase increase (see Table 2).

Table 2: Summary of Adverse Events Reported in $\geq 5\%$ of Mayzent treated patients at a rate of at least 1% higher than in patients receiving placebo

Adverse reaction	MAYZENT 2 mg (N=1099) %	Placebo (N=546) %
Headache ^a	15	14
Hypertension ^b	13	9
Transaminase increased ^c	11	3
Falls	11	10
Peripheral edema ^d	8	4
Nausea	7	4
Dizziness	7	5
Diarrhea	6	4
Bradycardia ^e	6	3
Pain in extremity ^f	6	4

Terms were combined as follows:

- Headache, tension headache, sinus headache, cervicogenic headache, drug withdrawal headache, and procedural headache.
- Hypertension, blood pressure increased, blood pressure systolic increased, essential hypertension, blood pressure diastolic increased.
- Alanine aminotransferase increased, gamma-glutamyl transferase, increased hepatic enzyme increased, aspartate aminotransferase increase, blood alkaline phosphatase increase, liver function test increased, hepatic function abnormal, liver function test abnormal, transaminases increased.
- Peripheral edema, joint swelling, fluid retention, swelling face
- Bradycardia, sinus bradycardia, heart rate decreased
- Pain in extremity and limb discomfort

POTENTIAL SERIOUS ADVERSE EVENTS

+ *Bradycardia, Bradyarrhythmia, and Atrioventricular Conduction Delays*

Siponimod may cause the heart rate to slow, especially after taking the first dose. This issue will be mitigated by administering an EKG post dose at the 6-hour mark to assess for any potential adverse events. In addition, BP/HR will be checked hourly for 6 hours to assess for potential bradyarrhythmia or adverse events.

+ *Infections*

Siponimod lowers the number of lymphocytes, which may increase the risk of serious infections. Lymphocyte levels will be monitored by measuring a Complete Blood Count with differential at each in-clinic study visit.

+ *Liver Injury*

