9. STUDY INTERVENTION DISCONTINUATION AND PARTICIPANT DISCONTINUATION/WITHDRAWAL

DISCONTINUATION OF STUDY INTERVENTION

A subject may discontinue study drug under any of the following circumstances:

- The subject wishes to discontinue study drug treatment for any reason.
- The subject experiences AEs that necessitate discontinuing study drug treatment. The Principal Investigator, medical monitor, and DSMB should be notified immediately.
- The investigator or DSMB decides to discontinue treatment for medical reasons. The reason for termination of study drug before study completion should be recorded in the CRF. At the time of study drug discontinuation, the End of Study Drug Visit should be administered. If the subject is not willing or able to return for all remaining study visits, they should be asked to return for the Week 52 and Week 78 visits, as well as returning all unused study drug. If this is not possible, they should be contacted by phone at Week 52 for the End of Study assessments (adverse events, and concomitant medications). The reason for withdrawal should be recorded in the case report form (CRF). The subject should complete the procedures for the Early Termination Visit, provided written consent to do so has not been withdrawn.

Subjects who discontinue or are withdrawn from the study following randomization:

- if they stop treatment (drug or placebo) before Visit 7, they will be replaced by new subjects
- if they stop treatment (drug or placebo) after Visit 7, they will not be replaced.

LOST TO FOLLOW-UP

To be considered lost to follow up, the study coordinator will make three documented attempts to contact the subject, who must also miss two scheduled visits. If these efforts are unsuccessful, a certified letter will be sent to the subject. If no response is received after this communication, then, the subject will be officially considered lost to follow up.

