10. STUDY ASSESSMENTS AND PROCEDURES

EFFICACY ASSESSMENTS

The main drug efficacy measure for this study is neurodegeneration (secondary objective). We will derive annual brain atrophy rates by comparing volumetric MRI (vMRI) values for the hippocampal, cortical, and global thickness. All 105 study participants will undergo vMRI at Baseline (Week 0) and after 6 months, 12 months, and 18 months.

To demonstrate clinical utility, it is necessary to show that a possible treatment for AD can slow down or reverse cognitive decline. Thus, our tertiary objective (and secondary efficacy endpoint) will assess cognition in all study subjects. For this, we will employ the recently created, high-sensitivity

Alzheimer’s Disease Composite Score (ADCOMS), which is recommended for mild AD in clinical trials of 12 months’ duration or longer⁴¹. Briefly, ADCOMS consists of 4 Alzheimer’s Disease Assessment Scale-cognitive subscale items (ADAS-Cog13), 2 Mini-Mental State Examination items (MMSE), and all 6 Clinical Dementia Rating-Sum of Boxes items (CDR-SOB)⁴¹. ADCOMS will be administered at specified time points throughout the study (refer to study table 1). Furthermore, to assess conversion to AD or reversion to normality, we will repeat the cognitive measurements at 18 months (Week 78). This time was selected because the calculated mean time for conversion from aMCI to AD in the literature ranges from 12-20 months¹⁶. Thus, measuring cognitive performance 18 months after the start of the trial should provide us with a good assessment of whether Sisonimod is effective at slowing down cognitive decline. A positive effect of Sisonimod on cognitive outcome measures would translate into increased ADCOMS scores at the end of dosing vs. Baseline and/or a slower decline than in placebo-treated subjects at month 18.

Additional objectives (exploratory efficacy endpoints) are (i) an additional assessment of cognitive performance via the ADCS-ADL test administered every 6 months; and (ii) the measurement of biomarkers in the CSF, blood, and saliva, to explore the possibility of using biofluid markers as proxy of drug efficacy. For example, since Sisonimod is an immunomodulator that prevents the egression of T lymphocytes from peripheral lymphoid organs, we should observe a decrease in circulating T lymphocytes and inflammatory markers in the blood samples we collect during the entire course of this clinical trial.

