Every effort will be made to ensure the privacy of participant PHI and confidentiality by utilizing secure EMR and databases. Paper copies are filed by number in accordance with professional standards of privileged information. All documentation and case reports forms are compliant with HIPAA regulations. Confidentiality is safeguarded by strict adherence to these standards.

- Safety Monitoring

An independent Data Safety Monitoring Board (DSMB) comprised of three members not associated with the study will be secured prior to starting the study. This group of experts advises NIH and the Sponsor/Investigator. During the trial, the DSMB will review cumulative study data to evaluate safety, study conduct, and scientific validity and integrity of the trial. ...

A Medical Monitor has been secured to provide medical expertise to the study team including answering investigator questions about the protocol, patient eligibility and the medical management of subject AE/SAE assessment/treatment, and/ or medical emergencies.

There will also be a Study Monitor who is responsible for monitoring the conduct of the clinical trial on a regular basis as per GCP and ICH guidelines. He/she will inspect the case report forms at regular intervals throughout the study to verify adherence to the protocol; completeness and accuracy of the data; and adherence to local regulations on the conduct of clinical research. The investigators agree to cooperate with the study monitor to ensure that any problems detected during these monitoring visits are resolved.

The study monitor will inspect site facilities (e.g., pharmacy, drug storage areas, laboratories) and review study-related records to evaluate the trial conduct and compliance with the protocol, GCP, and applicable regulatory requirements. Results of locally administered tests such as EKG tracings and local clinical laboratory reports will be retained as source documents. At the monitoring visits, the progress of the study will be discussed with the Investigator and/or the Study Coordinator and the informed consent forms and CRFs will be checked for completeness and accuracy. Subjects' source documents should be available for review.

The investigators will immediately inform the Medical Monitor and the DSMB in case of moderate to severe adverse events, as well as when an individual subject is temporarily removed from dosing due to hematologic signs of toxicity (e.g. thrombocytopenia and/or neutropenia). All early

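### On-study toxicity values are borrowed from the entry criteria, so a lymphocyte count below 1,000/mm³ is treated as indicating a severe event although the protocol expects the drug to lower lymphocytes

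*Protocol*

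**What the plan says.** Section 10 of the protocol, under Procedure Used in Case of Toxicity, fixes the reference values: "The hematologic or chemistry values indicative of severe AEs are those listed in exclusion criteria". Section 11, under Reporting Events to Participants, makes the same reference for hematologic values. It says participants will be told to stop the drug if blood or cardiac toxicity is found, and points back to the Section 10 procedure. In the synopsis, exclusion criterion 15 begins "Absolute lymphocytopenia of $<1,000" (per mm³).

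Once toxicity is suspected or shown to be due to siponimod, the drug is stopped for 7 days and blood is retested. If the retest is still abnormal, the subject is withdrawn. If it has improved, dosing restarts 0.25 mg lower and stays there. A second event repeats the cycle and a third means withdrawal.

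The protocol also describes what the drug does to lymphocytes:

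- Section 2.2: "Immuno-modulation is mostly achieved by preventing egression of lymphocytes from lymphoid organs".
- Section 3.1.1: "Siponimod lowers the number of lymphocytes, which may increase the risk of serious infections".
- Section 10, Efficacy Assessments: "we should observe a decrease in circulating T lymphocytes and inflammatory markers in the blood samples".

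Under Safety Monitoring in Section 10, the medical monitor and DSMB are told at once when a subject is "temporarily removed from dosing due to hematologic signs of toxicity (e.g. thrombocytopenia and/or neutropenia". Platelets and neutrophils are given there as examples only, and lymphocytes are neither named nor exempted.

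**The concern.** A limit written to screen entrants is reused to judge subjects on a drug that is expected to move that same measurement downward. A subject may enter with a count at or just above 1,000/mm³, so even a modest fall can carry the count across the line.

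Two things are at stake. The first is exposure: each triggered event takes the subject off drug for a week and then permanently below the 1 mg/day under test, or off drug altogether. Because the fall is a drug effect, this would happen mainly in the siponimod arm. The second is the reading of the primary results. Section 4 makes safety and tolerability the primary objective, and Section 12 reports treatment-related events, events by severity and events leading to discontinuation. An expected action of the drug, labelled severe by the toxicity rule, would enter those counts.

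**Working it through.** The protocol states no figure on this point that can be reproduced. The check sets the texts side by side and then follows the dose rule.

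**1. Is the link to lymphocytes explicit?** Yes. Sections 10 and 11 import the exclusion-criteria values, and exclusion 15 is one of them. The protocol gives no separate on-study lymphocyte limit and no exemption.

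**2. Is a fall expected?** A decrease is expected, but its size is not given. Sections 2.2 and 3.1.1 concern lymphocytes in general; the Efficacy Assessments text concerns circulating T lymphocytes, not the absolute count.

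**3. What does a triggered event do to the dose?** The rule is dose after event = dose at event − 0.25 mg, with a 1 mg/day target.

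| Event | Dose at event (mg/day) | Dose after (mg/day) | Share of target |
|---|---|---|---|
| First, at full dose | 1.00 | 0.75 | 75% |
| Second, after that cut | 0.75 | 0.50 | 50% |
| Third | 0.50 | withdrawn | 0% |
| First, during titration | 0.75 | 0.50 | 50% |
| First, during titration | 0.50 | 0.25 | 25% |
| First, during titration | 0.25 | 0 | 0% |

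The table assumes that the retest improves each time; otherwise the subject is withdrawn at once. The last row is a drafting gap: the text tells the subject to resume a dose that does not exist. It concerns any toxicity, not lymphocytes in particular.

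**4. How often can the rule be applied?** A blood count with differential is scheduled at Visits 3 to 12, while dosing can still change:

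- Visits 3 to 6 (Days 14, 28, 42, 56): 4
- Visit 7 (Day 70): 1
- Visits 8 to 12 (Days 112, 168, 224, 280, 336): 5
- Total: 4 + 1 + 5 = 10

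Visit 7 matters because of the replacement rule in Section 9: "if they stop treatment (drug or placebo) before Visit 7, they will be replaced by new subjects". Those who stop after it are not replaced.

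**5. Which baseline counts would cross the limit?** The size of the fall has to be assumed. A subject drops below 1,000/mm³ if the baseline is below 1,000 / (1 − fall):

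- 20% fall: 1,000 / 0.8 = 1,250/mm³
- 30% fall: 1,000 / 0.7 = 1,429/mm³
- 50% fall: 1,000 / 0.5 = 2,000/mm³

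The protocol does not say how many subjects would enter below these values, so no trigger rate follows.

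**The case against.** The strongest defence is that the rule is a prompt for judgement. Section 10 has investigators review every laboratory result for clinical significance and possible attribution to the drug, and a stop needs toxicity that is at least suspected to be drug-related. Section 11 requires clinical judgement in grading the severity of events the participant does not feel, with laboratory abnormalities as the example. Holds for hematologic toxicity go at once to the medical monitor and DSMB, so a run of needless holds would be seen. A cautious limit is also defensible: low lymphocytes carry an infection risk, and an effect can be both expected and a reason to hold drug.

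Much of this stands, and it rules out reading the limit as a mechanical stop. It does not remove the problem. The value is still described as indicating a severe event, a lymphocyte fall is by mechanism linked to the drug, and nothing tells the investigator how to treat an expected fall. Caution justifies having a lymphocyte limit, but not reusing the entry limit for it.

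Three stronger readings are tempting, and the protocol does not support them:

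- **That counts below 1,000/mm³ are expected.** The protocol expects a decrease and never says how far.
- **That the rule will cost power or MRI data.** No trigger rate can be derived. Subjects off drug who will not attend every visit are still covered: "they should be asked to return for the Week 52 and Week 78 visits". Both visits include volumetric MRI. Any effect on the efficacy population also turns on an unclear entry in Section 12, which gives Visit 12 as Week 8; in Table 1, Week 8 is Visit 6 and Visit 12 is Week 48.
- **That lymphocyte changes would be hidden in the safety tables.** Section 12 already reports events by preferred term, and laboratory changes, out-of-range values and shifts separately. Only the reasons for holds, cuts and stops are not set out.

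**Conclusion.** The point holds as a badly fixed dosing rule and should be corrected. The text makes a lymphocyte count below 1,000/mm³ an on-study value indicating a severe event, with no exemption, for a drug that the same protocol expects to lower lymphocytes. When the rule is applied, the result is fixed: a 7-day stop, then 75% and later 50% of the target dose, or withdrawal from dosing. It falls mainly on the active arm and labels an expected effect as severe toxicity.

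The frequency is unknown. It depends on baseline counts and a size of fall that the protocol does not give, and on how investigators use their judgement. The conclusion rests only on the direction of the effect, which is stated, and on the absence of a separate on-study limit. No claim is made about attrition, power or bias in the MRI comparison.

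**What to change.** Amend the two places that refer to the exclusion criteria, Procedure Used in Case of Toxicity in Section 10 and Reporting Events to Participants in Section 11:

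- State that a lymphocyte count below the 1,000/mm³ entry limit is an alert for review and repeat testing, and not by itself a toxicity event.
- Set a separate, lower on-study hold limit, agreed with the medical monitor and the DSMB. The trigger is then a count below that limit confirmed on repeat, or a low count with clinical infection.
- Record the reason for every hold, dose cut and stop, and report the lymphocyte-driven ones separately. The laboratory shift tables already planned cover the counts themselves.
- As a minor clarification, state that after an event on 0.25 mg/day dosing is not resumed.

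The cost is amendment wording in two places and one added field with its summary. The downside is real but small: some subjects with counts between the new limit and 1,000/mm³ stay on drug, so infection monitoring at each visit must continue.
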